## 10.7.2 Duration of Response

Duration of overall response: The duration of overall response is measured from the time measurement criteria are met for CR or PR (whichever is first recorded) until the first date that recurrent or progressive disease is objectively documented (taking as reference for progressive disease the smallest measurements recorded since the treatment started).

The Duration of Overall Complete Response (CR): measured from the time measurement criteria are first met for CR until the first date that progressive disease is objectively documented.

**Duration of Stable Disease (SD):** Stable disease is measured from the start of the treatment until the criteria for progression are met, taking as reference the smallest measurements recorded since the treatment started, including the baseline measurements.

## 10.8 Response Criteria for CNS Tumours

# 10.8.1 Special Considerations for Tumour "Pseudo-progression" Phenomena

In Neuro-Oncology, progressive imaging findings in patients receiving immunotherapy pose challenges in interpretation of those radiological findings and may result in premature discontinuation of potentially beneficial therapy (Okada, 2015).

Correct interpretation of progressive imaging findings after administration of immunotherapy is essential because early progressive radiographic changes do not always preclude subsequent therapeutic benefit.

Two main explanations exist for a possible disconnect between early worsened imaging findings and subsequent therapeutic benefit. First, effective immune responses might need time to evolve, and early imaging might reflect true progressive disease, including the development of new lesions. Nonetheless, once induced, an effective anti-tumour immune response might subsequently lead to clinical benefit. Second, because the mode of action might include an inflammatory response in areas of macroscopic and microscopic infiltrative tumour, localized inflammatory responses might mimic radiological features of tumour progression with increased enhancement and oedema (Bouffet, 2016).

For cases of pseudo-progression, histopathology typically shows remarkable immune-cell infiltration, such as CD8+ T lymphocytes, but not mitotically active tumour cells. Further radiological confirmation to define progressive disease is an important, novel aspect of immune-related response criteria, together with the need of follow-up imaging to confirm a radiographic response (Okada, 2015). For example, the temporal window for TMZ/RT→TMZ pseudo-progression generally peaks within three months, the time frame for immunotherapy-associated pseudo-progression remains to be defined and may differ by class of ICI (Okada, 2015). The current RANO guidelines, do not permit treatment continuation beyond actual tumor progression because subsequent therapeutic benefit supporting this practice has not been documented for oncology treatments other than immunotherapies, but the iRANO do.

Neuro-oncology criteria that are based on guidance for determination of tumor progression outlined by the immune-related response criteria (irRC) and the response assessment in neuro-oncology (RANO) working group, deemed iRANO have developed and as such, for CNS tumours treated with ICI, iRANO response criteria guidelines will be used (Wen, 2010; van den bent, 2011; Okado, 2015; Lin, 2015) are used to evaluate tumour response.

#### 10.8.2 Selection of Target and Non-Target Lesions

For most CNS tumours, only one lesion/mass is present and therefore is considered a "target" for measurement/follow up to assess for tumour progression/response. If multiple measurable lesions are present, up to five (5) should be selected as "target" lesions. Target lesions should be selected on the basis of size and suitability for accurate repeated measurements. All other lesions will be followed as non-target lesions. The lower size limit of the target lesion(s) should be at least twice the thickness of the slices showing the tumour to decrease the partial volume effect (e.g., 8 mm lesion for a 4-mm slice).

Any change in size of non-target lesions should be noted, though does not need to be measured.

## 10.9 Response Criteria for Target Lesions

Response criteria are assessed based on the product of the longest diameter and its longest perpendicular diameter. Development of new disease or progression in any established lesions is

considered PD, regardless of response in other lesions - e.g., when multiple lesions show opposite responses, the progressive disease takes precedence.

For patients with early progressive imaging findings (within six (6) months from initiation of the immunotherapy), including patients who develop new lesions but who do not have substantial neurological decline, confirmation of radiographic progression by follow-up imaging should be sought three (3) months after initial radiographic evidence of progressive disease to decrease the likelihood of prematurely declaring progressive disease in patients with pseudo-progression or delayed response.

Imaging within the 3-month follow-up can be done as medically appropriate at the discretion of the treating physician.

Patients with confirmation of further radiographic progression based on a comparison with the scan that first showed evidence of disease progression (new reference scan) should be classified as having progressive disease with the date of disease progression back-dated to the first date that the patient met criteria for radiographic progression. In those patients, non-responsiveness to treatment should be assumed and therapy discontinued.

Patients who develop substantial new or worsened neurological deficits not due to comorbid events or a change in co-administered medication at any time within the 3-month follow-up window should be designated as non-responsive to treatment and should discontinue immunotherapy. For these patients, the date of actual tumour progression should also be backdated to the date when radiographic progressive disease was initially identified.

If follow-up imaging does not confirm further disease progression compared with the scan of the tumour that first showed initial progressive changes, but instead there is stabilization or reduction in tumour burden, treatment should be continued or resumed in the absence of increased corticosteroid dosing.

Patients who develop worsening radiographic findings compared with the pre-treatment baseline scan more than 6 months from starting immunotherapy are expected to have a low likelihood of ultimately deriving clinical benefit and should be regarded as non-responsive to treatment with a recommendation to discontinue therapy.

	start of immunotherapy).	start of immunotherapy).
Is a repeat scan required to confirm radiographic	Yes	No
PD for patients without clinical decline?		
Minimal time interval for confirmation of	≥ 3 months	N/A
progression for patients without significant		
clinical decline?		
Is further immunotherapy treatment allowed after	Yes	N/A
initial radiographic PD (if clinically stable)		
pending progression confirmation?		
Does a new lesion define PD?	Yes	Yes

## 10.9.2 Confirmation of Radiographic Progression

Traditional imaging criteria to define PD may be less reliable and could lead to premature discontinuation of potentially beneficial therapy. Early increases in lesion size or new lesions do not define PD unless further progressive changes are confirmed upon follow-up imaging, provided that patients are not experiencing clinical decline. Particularly for indications such as glioblastoma, where effective therapeutic interventions are limited, and durable responses are elusive, continuation of immunotherapies beyond initial progression may lessen the likelihood of prematurely discontinuing potentially effective therapy (Okada, 2015; Bouffet, 2016).

Spider-plots describing changes in tumor volume over time for solid tumor patients undergoing immune checkpoint blockade demonstrate that early progressive radiographic findings typically stabilize or improve within three months for the majority of patients who ultimately derive clinical benefit (Topalian, 2012; Hamid, 2013; Brahmer, 2012). Based on these observations, among patients with early progressive imaging findings including the development of new lesions who are not experiencing significant neurologic decline, confirmation of radiographic progression via follow-up imaging should be sought no sooner than three months after initial radiographic evidence of PD is detected, to decrease the likelihood of prematurely declaring PD in patients with pseudo-progression or delayed response. Imaging within the three (3)- months follow-up period can be performed as medically appropriate at the discretion of the treating clinician. Among those with confirmation of further radiographic progression based on comparison to the scan which first revealed evidence of progression, or who exhibit significant clinical decline at any time, should be classified as PD with the date of disease progression backdated to the first date that the patient met criteria for radiographic progression. Such patients should be discontinued from their current immunotherapy regimen.

If follow-up imaging does not confirm further progression compared to the scan which first revealed initial progressive changes, but instead reveals stabilization or reduction in tumor burden, in the absence of increased corticosteroid dosing, treatment should be continued or resumed (see *Figure 4*).

[figure not shown]
Patients with significant neurologic decline, regardless of imaging findings, are deemed to have PD, providing their decline is not attributable to co-morbid events such as seizures or changes in medication, notably decreased corticosteroid dosing. For such patients, radiographic

confirmation of PD is neither necessary nor appropriate and their date of PD is the date they developed significant neurologic decline attributable to underlying tumor.

Anecdotal reports of glioma patients treated with tumor vaccination and ICI therapy have described pseudo-progressive radiographic findings that also typically manifest within six months of treatment initiation (Hoos, 2010; Sampson, 2010; Pollack, 2014).

Conversely, there is no evidence that patients develop delayed clinical benefit or radiographic response if they develop progressive radiographic findings more than six (6) months after initiating immunotherapy.

**Figure 4.** iRANO treatment algorithm for the assessment of progressive imaging findings in patients with neuro-oncological malignancies undergoing immunotherapy (Okada, 2015).

#### **10.9.3 Non-Target Lesions**

## 10.9.3.1 Tissue Acquisition to Aid Response Assessment

In uncertain cases in which acquisition of tumor histopathology via biopsy or resection is considered feasible, pathological assessment may be considered to clarify the etiology of progressive imaging findings. Discussion with the Study Chair or Co-chair prior to surgery is strongly encouraged if timing permits. If pathology confirms a predominance of recurrent tumor, the etiology should be considered to be true progression. For cases where no evidence of viable tumor is detected, or where a prominence of gliosis/inflammation with limited viable tumor is observed, the etiology should be considered consistent with treatment effect, such patients should be classified as stable and allowed to continue therapy.

### **10.9.3.2** Response Criteria for Non-Target Lesions

Complete Response (CR): Disappearance of all non-target lesions.

Incomplete Response/Stable Disease (IR/SD): The persistence of one or more non-target lesions.

**Progressive Disease (PD):** The appearance of one or more new lesions and/or unequivocal progression of existing non-target lesions confirmed on follow-up imaging  $\geq 3$  months after initial radiographic progression with requires no new or significantly worsen neurological deficits not due to co-morbid event or concurrent medication  $\leq 6$  months from initiation of nivolumab.

#### 10.10 Response Criteria for Tumour Markers (if available)

Tumour markers will be classified simply as being at normal levels or at abnormally high levels.

# 10.11 Response Evaluation for Patients Receiving Therapeutic Corticosteroids

During the course of treatment, if pseudo-progression occurs, higher doses of corticosteroids may be necessary to control symptoms, and this may impact on disease response evaluation. Patients who require increased corticosteroids within two weeks of MRI assessment

relative to the dose taken at the time of the prior assessment, cannot be classified as CR, PR, or SD and should be classified as non-evaluable at that time point. Conversely, patients who decrease corticosteroids within two weeks of MRI assessment, relative to the dose taken at the time of the prior assessment, cannot be classified as PD and should be classified as non-evaluable.

## **10.12** Overall Response Assessment

The overall response assessment takes into account response in both target and non-target lesions, the appearance of new lesions and normalization of markers (where applicable), according to the criteria described in the table below. The overall response assessment is shown in the last column, and depends on the assessments of target, non-target, marker and new lesions in the preceding columns (see *Table 12*).

**Table 12.** Overall response for CNS lesions.

Target	Non-Target	Markers	New Lesions	Overall Response
Lesions	Lesions			
CR	CR	Normal	No	CR
CR	IR/CD	Normal	No	PR
CR	Non-PD	Abnormal	No	PR
PR	Non-PD	Any	No	PR
CD	Non-PD	Any	No	CD
PD	Any	Any	Yes or No	PD
Any	PD	Any	Yes or No	PD
Any	Any	Any	Yes	PD

## 10.13 Response Criteria for Patients with AML

The AML response criteria are derived according to Creutzig, *et al.* (2004, 2012) with some revisions from the AML International Working Group (IWG) Criteria (Cheson, 2003).

The following definitions will be used:

**Complete remission (CR):** All of the following must be achieved:

- BM blasts <5% (M1 BM);
- Absence of circulating blasts or extramedullary disease;
- Absolute neutrophil count (ANC)  $\geq 1.0 \times 10^9 / L$ ;
- Platelet count  $\geq 80 \times 10^9/L$ .

Occasionally, a rare peripheral blood blast may be identified during marrow regeneration; however, the marrow must be M1 status and with no Auer rods. Flow cytometry may also be useful to distinguish between leukemia and a regenerating BM. There is no requirement for BM cellularity.

Morphological CR with partial recovery of platelet count (CRp): All of the following must be achieved:

- BM blasts <5% (M1 BM) with no Auer rods;
- Absence of circulating blasts or extramedullary disease;
- Recovery of ANC  $\geq 1.0 \times 10^9 / L$ ;
- Platelet transfusion independence (defined as, no platelet transfusions for 1 week).

Morphological CR with incomplete count recovery (CRi): All of the following must be achieved:

- BM blasts <5% (M1 BM) with no Auer rods;
- Absence of circulating blasts or extramedullary disease;
- All CR criteria except for residual neutropenia (<1.0 x 10^9/L) or thrombocytopenia (<80 x 10^9/L) without platelet transfusion independence (defined as, no platelet transfusions for 1 week).

#### Cytogenetic complete remission (CRc):

- The patient must also have attained and be assigned morphologic response of CR or CRp or CRi as defined above.
- Must have a revision to a normal karyotype with a minimum analysis of 20 metaphases.

**Partial Response (PR):** A decrease of at least 50% blasts percentage (to M2: 5% to 25%) in the BM aspirate. BM must have adequate cellularity (e.g., > 15%) to determine response. PR status will not be included in calculation of response to the regimen.

A repeat BM aspiration after several weeks may be required to distinguish between a PR and increased blasts caused by BM regeneration. A value of < 5% blasts may also be considered a PR if Auer rods are present.

#### **Treatment Failure (TF):**

- Failure to achieve CR or CRi
  - Any M2 (5-25% blasts) or M3 (5-25% blasts) BM aspirate that does not qualify for PR status;
  - M1 (5% blasts) BM aspirate with evidence of circulating blasts or extramedullary disease;

**Relapse:** Morphologic relapse after CR/CRp/CRi is achieved and documented, defined as:

- A reappearance of leukemic blasts in the peripheral blood or ≥ 5% blasts (M1) in BM not attributable to any other cause (such as, BM regeneration after consolidation therapy).
- If there are no circulating blasts, but the BM contains 5% to 25% blasts (M2)
  - A repeat BM performed at least a week later is necessary to distinguish relapse from BM regeneration.
- The reappearance or development of cytologically proven extramedullary disease;
  - Molecular and/or genetic relapse is characterized by reappearance of a cytogenetics or molecular abnormality.

Should flow cytometry analyses suggest relapse (by the reappearance of a similar immunophenotype to the original leukemia) in the presence of < 5% blasts, or  $\ge 5\%$  blasts in a regenerating marrow, a repeat BM aspirate performed at least a week later is necessary to confirm relapse by morphologic methods. In such instances, the date of recurrence is defined as the first date that  $\ge 5\%$  blasts were observed (in BM).

**Unevaluable:** Aplastic or severely hypo-cellular marrow with any blast percentage. In this instance, marrow evaluation should be repeated weekly until response determination can be made through at least Day 49.

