	response criteria for solid tumours (revised for neuroblastoma using the				
	revised INRC), iRANO response criteria for CNS malignancies, RECIL				
	2017 response criteria for lymphomas, revised criteria according to				
	Creutzig, et al. (2012) for acute myeloid leukemia (AML; see Section				
	10.13), and response criteria as specified in Section 10.14 for acute				
Criteria for	lymphoblastic leukemia (ALL).				
Efficacy	Patients with response of 'stable disease' (SD) will also be reported as part				
Evaluation:	of the final analysis of clinical benefit, but will not contribute to the				
	primary efficacy outcome measure.				
	Secondary efficacy outcome measures:				
	PFS is defined as the time from the first dose of the study drug				
	administration to the occurrence of disease progression or death from any cause during the study.				
	OS is defined as time from first dose of study drug to death from any				
	cause.				
	A safety evaluation by the Safety Committee will be performed after				
Criteria for	Patient 1-Cycle 1, Patient 4-Cycle 1, Patient 7-Cycle 1, and Patient 10-				
Safety	Cycle 1. Enrollment will be held after each time point until a safety				
Evaluation:	evaluation of adverse events (AE) and serious adverse events (SAE)				
	confirms it is safe to resume enrollment.				
	confirms it is safe to resume enrollment.				

Toxicities will be described and defined in paediatric patients, focusing on SAEs, using the National Cancer Institute Common Terminology Criteria for Adverse Events (NCI CTCAE), version 4.03. Toxicities (drug-related AEs) of any grade, plus all Grade  $\geq$  3 AEs, all Grade  $\geq$  3 laboratory toxicities and all SAEs as defined in *Section 12* will be collected for this study.

The initial aim for this pilot study was to accrue 20 paediatric patients with biallelic mismatch repair disease (bMMRD) tumours. Following amendment, the study inclusion criteria are expanded to include those with hypermutant tumours (as determined by estimation of TMB by targeted next-generation gene sequencing), as well as patients with CMMRD tumours. Consequently, the total enrollment will be increased to 50 patients.

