## 4.2.2 Part II - Treatment and Companion Biomarker Inclusion Criteria

In order to participate in **Part II**, patients must meet the following criteria:

- **1. Consent/ Assent:** Patient and Legally Acceptable Representative (LAR; such as a parent or guardian, as applicable) must be willing and able to provide written informed consent/assent for the trial as per local requirements.
- **2. Confirmation of Hypermutation or Proof of RRD:** patient must have completed and verified a sufficient TMB level or have proof of RRD diagnosed in the appropriate lab, as outlined in the *Lab Manual*.
- 3. Age: patients must be ≥ 12 months and < 25 years of age at the time of Part II enrollment.

  Local centres are only obligated to treat/ admit patients in accordance their age range capabilities.
- **4. Diagnosis:** patients must have had histologic verification of malignancy at the time of initial diagnosis or at relapse (as specified above). Patients with multiple concurrent and/or sequential neoplasms are eligible, including CNS and haematological malignancies.
- **5. Disease status:** patients must have either measurable or evaluable disease in accordance with criteria as outlined in *Section 10*. Tumour lesions situated in a previously irradiated area are considered measurable if progression has been demonstrated in such lesions.
- **6. Treatment options:** patient's current disease state must be one for which there is no known curative therapy or therapy proven to prolong survival with an acceptable quality of life. Chemotherapy-naïve patients will be eligible in cases where first-line therapy does not include chemotherapy (e.g. surgery alone for management of ependymoma).
- 7. Performance status: Karnofsky  $\geq 50\%$  for patients > 16 years of age or Lansky  $\geq 50$  for patients  $\leq 16$  years of age. Patients who are unable to walk because of paralysis, but who are

up in a wheelchair, will be considered ambulatory for the purpose of assessing the performance score.

- **8. Previous treatment:** patients must have fully recovered from the acute toxic effects of all prior anti-cancer therapy.
  - **a. Myelosuppressive chemotherapy:** at least 21 days after the last dose of myelosuppressive chemotherapy (42 days if prior nitrosourea).

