#### **10.14** Response Criteria for the Patients with ALL

**Complete Remission (CR):** All of the following must be achieved:

- BM blasts <5% (M1 BM and adequate marrow cellularity);
- Absence of circulating blasts or extramedullary disease;
- Absolute neutrophil count (ANC)  $\ge 0.75 \times 10^9 / L$
- Platelet count  $\geq 75 \times 10^9/L$

Qualifying marrow and peripheral counts should be performed within 1 week of each other.

Morphological CR with partial recovery of platelet count (CRp): All of the following must be achieved:

- BM blasts <5% (M1 BM);
- Absence of circulating blasts or extramedullary disease;
- Recovery of ANC ≥750/mcL
- Insufficient recovery of platelets (< 75 000/mcl).

Morphological CR with incomplete count recovery (CRi): All of the following must be achieved:

- BM blasts <5% (M1 BM);
- Absence of circulating blasts or extramedullary disease;
- No recovery of ANCs (ANC < 750/mcl)
- Insufficient recovery of platelets (< 75 000/mcl).

**Partial Remission (PR):** All of the following must be achieved:

- Complete disappearance of circulating blasts and achievement of M2 BM status (5-25% blasts), without new sites of extramedullary disease;
- Recovery of ANCs (ANC > 750 mcL).

**Partial Remission** – **Cytolytic (PRCL):** Complete disappearance of circulating blasts and achievement of at least 50% reduction from baseline in BM blast count.

**Stable Disease (SD):** The patient does not satisfy the criteria for PD, or has recovery of ANC > 750 mcL and fails to qualify for CR, CRp, or PR.

**Progressive Disease (PD):** An increase of at least 25% in the absolute number of circulating leukemic cells, measured pre-therapy or during the first 14 days following start of therapy; or other laboratory or clinical evidence of PD, with or without recovery of ANC or platelets.

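### The leukaemia response definitions contradict themselves: ALL stable disease overlaps progression, AML blast bands conflict, and AML has no progression category

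*Protocol*

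**What the plan says.** Leukaemia patients can enter. Section 4.2.2, item 4, states: "Patients with multiple concurrent and/or sequential neoplasms are eligible, including CNS and haematological malignancies".

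PFS is a secondary outcome for all patients. The Synopsis, under Criteria for Efficacy Evaluation, starts the clock at the first dose and runs it from that "administration to the occurrence of disease progression or death from any cause during the study". The same entry says that SD will be reported in the final analysis of clinical benefit but will not count towards the primary outcome.

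**ALL (Section 10.14).** The SD entry, given here without its final item (partial remission), is: "The patient does not satisfy the criteria for PD, or has recovery of ANC > 750 mcL and fails to qualify for CR, CRp, or". The PD entry directly below requires a rise of at least 25% in circulating leukaemic cells, counted before therapy or in the first 14 days, or other laboratory or clinical evidence. It adds that recovery of neutrophils or platelets makes no difference.

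**AML (Section 10.13).** The categories are CR, CRp, CRi, CRc, PR, Treatment Failure, Relapse and Unevaluable. PR is "A decrease of at least 50% blasts percentage (to M2: 5% to 25%) in the BM aspirate". Treatment Failure opens with "Failure to achieve CR or CRi" and then lists "Any M2 (5-25% blasts) or M3 (5-25% blasts) BM aspirate that does not qualify for PR status". Relapse is available only after CR, CRp or CRi, and its first criterion includes "≥ 5% blasts (M1) in BM not attributable to any other cause".

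**The concern.** Response categories should be mutually exclusive, and one blast label should mean one range throughout. Neither holds in these two sections. SD feeds the clinical-benefit report, so a rule that lets a progressing ALL patient qualify as SD can put that patient on the wrong side of the report. PFS ends at progression, so a disease section that never says what progression is leaves the event and its date to whoever grades the patient. Sites and the analysis team could then classify the same patient differently while each follows the text.

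**Working it through.** The protocol states no figure on this point, so the check compares the definitions with one another.

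**1. ALL: SD against PD.** As written, SD = (not PD) or (ANC > 750 and none of CR, CRp, PR). The table runs this rule over the possible states, taking PD and response as unable to coexist.

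| PD met | ANC > 750 | CR, CRp or PR | SD as written | Conflict |
|---|---|---|---|---|
| no | no | no | yes | none |
| no | no | yes | yes | SD and response |
| no | yes | no | yes | none |
| no | yes | yes | yes | SD and response |
| yes | no | no | no | none |
| yes | yes | no | yes | SD and PD |

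The last row is the overlap with progression: the second limb admits the patient to SD, and PD applies whether or not the ANC has recovered. The response conflicts come from the first limb, which admits everyone without PD. The second row is almost empty in practice: CR and CRp need an ANC of at least 750 and PR needs one above 750, so it arises only at exactly 750. The fourth row is the ordinary responder. CRi and PRCL (cytolytic partial remission) are missing from the SD exclusion altogether, so the first limb labels those patients SD as well.

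Under a rule of SD = (not PD) and (none of CR, CRp, CRi, PR, PRCL), SD remains only in the first and third rows, for patients in none of those categories, and no row conflicts.

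**2. AML: the blast bands.**

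- CR, CRp and CRi: M1 is below 5%.
- PR: M2 is 5% to 25%.
- Treatment Failure: M2 is 5–25% and M3 is also 5–25%; the next item prints M1 as 5%.
- Relapse: 5% or more is labelled M1, and the following item gives 5% to 25% as M2.

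So M3 is indistinguishable from M2, a marrow above 25% has no band under Treatment Failure, a marrow at exactly 5% is both M1 and M2, and the relapse line's M1 contains the whole of M2 and none of the M1 used for remission.

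This changes no Treatment Failure classification above 25%, because the opening line of that entry (no CR or CRi) already captures such a marrow.

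**3. AML: progression.** Solid tumours (10.4, 10.5), neuroblastoma (10.6, 10.7), CNS tumours (10.9), ALL (10.14) and lymphoma (10.15.3) each define PD. Section 10.13 does not. For an AML patient who never reaches CR, CRp or CRi and whose blasts rise:

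- Relapse is unavailable, because it requires a prior remission.
- Treatment Failure applies, but it has no time point and is nowhere called progression.
- No other category in 10.13 describes worsening.

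That patient therefore has no defined, dated progression event in Section 10.13.

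**The case against.** A reader might infer that leukaemia progression cannot be derived at all. The documents do not support that. ALL has a PD definition, and giving it precedence would settle the overlap; since PD disregards ANC recovery, that is probably what was intended. AML relapse after remission is defined, with a dating rule where flow cytometry suggests relapse. The gap is confined to AML patients who never remit.

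A reader might also infer that PFS in those patients must equal overall survival or be censored. That goes too far. The Synopsis defines PFS by progression, not by a category in 10.13, and Section 13.2, item 1, recognises clinical evidence of progressive disease in any patient. AML progression is unspecified rather than excluded. The mapping from response category to PFS event could also sit in a statistical analysis plan that is not at hand.

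A third tempting reading is that the SD/PD overlap is the usual case, because eligibility requires an ANC of at least 0.75 x 10^9/L. A baseline requirement does not show the count at progression, so that is inference.

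Finally, PFS is secondary and Section 11 attaches no test or decision rule to it.

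All of this limits the size of the point. It does not remove it: the ALL rule and the blast bands are errors in the protocol's own text, whatever a later plan adds.

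**Conclusion.** The point holds in a limited form. The ALL SD rule is not exclusive of PD or of response, and the AML blast bands contradict the CR and PR definitions in the same section. AML alone lacks a progression category, which leaves never-remitting patients without a defined, dated event in 10.13.

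The consequences are possible misreporting of SD and clinical benefit in ALL, and an unspecified progression event for secondary PFS in AML non-remitters. The blast-band error must be corrected, but by itself it does not change PFS. The primary response rate and the cohort decision rules count CR and PR and are not altered, provided that a responder who also meets the SD wording is still counted as a responder.

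The effect cannot be expressed as a number of patients or events: the protocol plans 50 patients across all diagnoses and does not say how many will have leukaemia. The conclusion rests on reading the definitions literally and assumes no precedence rule, since neither section states one.

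**What to change.** 1. **Section 10.14.** Define SD as not meeting PD and not qualifying for CR, CRp, CRi, PR or PRCL. Replace the *or* with *and*, and drop the ANC clause from the SD rule. If that clause stayed beside an *and*, a patient with no progression, no remission and no neutrophil recovery would have no category.
2. **Section 10.13.** Reconcile M1, M2 and M3 with the CR and PR definitions, which already use below 5% for M1 and 5% to 25% for M2 and so leave only the range above 25% unassigned. Correct the M1 figure under Treatment Failure and remove the M1 label from the relapse line.
3. **PFS.** State which existing AML and ALL categories (for example relapse, treatment failure or PD) count as the progression event and how each is dated. Treatment Failure would need a time point if it is included. The ALL circulating-cell threshold should not be carried into AML: Section 10.14 ties it to the period before therapy or the first 14 days, so it would not define later progression.

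The cost is protocol wording. The blood counts and marrow evaluations are already scheduled in Section 8.2. Any leukaemia patient already graded should have the category rechecked against the corrected text.
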